At the in-person version of the initial meeting, The participant will review the consent form in person with the research coordinator present, have an opportunity to ask questions, then decide if they would like to participate in the study. For those interested in participating, they will sign a written consent form and receive a copy for their records. A copy will also be kept as part of the study records. Participants will also be given a one page info sheet, which briefly explains the study and who to contact with questions or concerns. Participants will also be provided explanation and opportunity to discuss the site-specific additional, optional testing (see Appendix), which would take place at the end of the in-person study visits. They will need to complete an additional consent form for the additional, optional testing. Their agreeing to, or declining, the additional, optional testing will not impact their participation in the main study. Participants will be informed of their right to withdraw from participation at any time, for any reason, and will be encouraged to ask any questions at any time. The study coordinator will be trained in confidentiality, informed consent procedures, and other aspects of human subject protection.

Virtual Consent

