6.2 Randomization and Blinding of Study Intervention

N/A Participants will be randomized equally between MM and CBT arms (1:1 ratio), using a permuted blocks of random size strategy, stratified by site and prepared by the study statistician. Sealed envelopes with group assignment will be distributed consecutively; participants will break the seal after completing the baseline assessments.

Although participants, therapists and outcome assessors cannot be blinded to the study intervention, investigators and analysts will be blinded to the group status until the first stages of analysis and reporting are completed.

7 Study Procedures

The initial eligibility screening will take place by phone or in person (see Section 5.4.2 for details). Those eligible and interested in participation will meet in person with the study coordinator.

In-Person Consent/Enrollment/Baseline/Randomization

During the in-person meeting at baseline, eligibility will be confirmed. Eligible, interested individuals will complete the written informed consent procedures and be assigned a study ID number (approximately 20 minutes to complete, on average). Then they will complete the baseline questionnaires (approximately 55 minutes to complete, on average), followed by a brief videorecorded activity focused on the assessment of physical function (approximately 10 minutes to complete). This videorecorded activity will involve the participant performing the standardized Timed Up and Go (TUG) test, evaluating a participant ability to stand up from a chair, walk 3 meters, before walking back to the chair and sitting down,^{110,111} and a brief interview about the impact of back pain and opioid therapy, and expectations/impact of the study. Then participants will be randomized (1:1 block scheme prepared by the study statistician) to the MM or CBT groups, and receive information about details and scheduling of their respective interventions. All baseline questionnaires can be completed verbally, electronically, or on paper if the participant requests it.

Virtual Consent/Enrollment/Baseline/Randomization

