In addition to the study contact for the intervention sessions and outcome data collection, participants will be contacted approximately every 2-4 weeks (and additionally as needed for engagement purposes) to "check in", to inquire about how the study is going for them and if they have any questions, and answer questions they may have.

Optional, Additional Testing (in-person participants only)

Participants who are eligible for it will be given the choice to consent to participate in optional, additional testing, when offered in person. The testing will be site-specific, conducted at the end of the two in-person study assessment visits (at baseline and exit). Each test will take on average approximately 15 minutes. For Madison participants, this test will involve a breath counting test using a laptop to measure mindful attention; for Boston participants, it will involve application of mechanical pressure to several body sites (pressure similar to the sensation of pressing a fingertip with steadily increasing pressure against the skin) and submerging hand in cold water at the temperature of 4 degrees centigrade (approximately the temperature of ice water) for no more than 2 minutes, to measure pain sensitivity and modulation; for Salt Lake City participants, it will involve engaging in computer-based emotional regulation and cue reactivity tasks using images from the International Affective Picture System (IAPS) and photos taken from media libraries on the internet. IAPS Images will include negative (angry faces, violent scenes), pain-related (accident scenes, injuries, medical conditions), and neutral images; opioid-related images (pills, pill bottles) will be taken from media libraries. The photographs will not be any more explicit than those seen in an R-rated movie. It is very unlikely that distress from the photos would exceed a distress which would occur on an everyday basis, given that the images we use are similar to images seen in our usual environments. Psychophysiological assessment (heart rate variability, respiration, facial activity) will be measured during these tasks.

The study manager, site managers, the PI, site-PIs and Co-Is will be responsible for monitoring and coordination of all study activities.

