7.2 Study Visits

7.2.1 Screening/Baseline:

Potential participants will be identified through the methods described in Section 5.4.1. Potential participants, meeting pre-specified eligibility criteria, will be sent invitation letters with opt-out/response card; those not opting out will be contacted by phone by the study coordinator. Potential participants will also be able to obtain the information about the study through their clinicians, study brochures, and media advertisement, and contact the study coordinator directly to inquire about the study.

A study coordinator will call potential subjects to introduce the study and answer any questions. During this conversation, the researcher will read an informational statement describing the study and informing the participant of the risks and his/her rights as a participant, in particular the right to cease participation at any time without any repercussion or loss of benefits. The researcher will then seek to obtain the participant's verbal consent to proceed with eligibility screening. Screening will be based on self-report and take 10-15 minutes to complete (see Appendix for the scripted text). Those not eligible for or interested in study participation will be referred back to their usual providers.

Those who are eligible and interested will be invited to schedule a virtual or in-person meeting with the study coordinator to complete the screening, enrollment and consent procedures. This meeting will be held virtually or at a clinical or research facility in person. The study participant will be assigned a unique, study-specific ID number, and complete baseline assessments (questionnaires, followed by the videorecorded activity). Enrolled participants will also be given the option to sign an additional consent for optional additional testing, when in person visits are offered (see Section 7, Study Procedures).

Finally, the participant will be randomized to one of the study arms and scheduled for the MM or CBT intervention. A reminder letter, emphasizing the importance of research participation, will be sent to the enrolled participants prior to the intervention start date and/or handed out at the beginning of the intervention course.

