For those screened but not enrolled in the study, all identifiable information will be destroyed. We will retain non-identifiable information collected during the screening process to help determine main reasons for ineligibility or declining participation and inform future research. All potential subjects will provide verbal consent for obtaining these data at the beginning of their screening process.

7.2.2 Follow up:

Table 4. Acceptable Window for Study Visits (including weekends)

| Visit | Window | Activities |
|---|--|--|
| Initial Visit (Screening, Enrollment, Baseline Assessment, Randomization) | + up to 12 weeks from the last contact / screening | Virtual or in-person visit. Confirm eligibility; consent/HIPAA authorization form; enrollment; completion of baseline questionnaires and videorecorded activity; randomization; scheduling for the intervention; compensation. |
| 3-month follow-up | + up to 8 weeks from due date | Online/phone/mail (if necessary) questionnaires, compensation mailed |
| 6-month follow-up | + up to 8 weeks from due date | Online/phone/mail (if necessary) questionnaires, compensation mailed |
| 9-month follow-up | + up to 8 weeks from due date | Online/phone/mail (if necessary) questionnaires, compensation mailed |
| 12- month follow-up (exit) | + up to 16 weeks from due date | Virtual or in-person visit. Completion of exit questionnaires and videorecorded activity, compensation. Completion by phone or mail if necessary. |
| In-depth qualitative interview (subset of 80 participants) | + up to 16 weeks from due date | Qualitative interview by phone; compensation mailed. |

The final study visit, the “Exit Visit”, will occur approximately 12 months from the intervention start date for a given participant (Table 4). A subset of participants who completed the final study visit will be invited to undergo an in-depth qualitative interview by phone about their experience with the study intervention and its effects (Table 4).

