Madison Site: Madison Site Participants will be offered the breath counting test, developed by [name] team.⁹⁸ This test will provide an objective evaluation of participant ability to sustain attention and complement the self-reported measures of mindfulness (Mindfulness Attention Awareness Scale survey) and logs of at-home practice. We hypothesize that participants in mindfulness meditation group will achieve greater improvements in their ability to sustain attention (better accuracy of breath counting) compared to those in the CBT group; this may mediate potential differences in treatment effects. For this test, participants will be instructed to "be aware of the movement of breath" and count their breaths in cycles from one to nine. They will be asked to press one of two different keys on the laptop/computer indicating which breath they are on, and a third key if they miss a breath. During the test, a set of 3 probes will appear on the screen inquiring about attention and breath count. This test will be administered by a trained research staff.

Boston, MA (Site PI: [name]):

Boston Site Participants will be offered the standardized Quantitative Sensory Testing (QST) to non-invasively measure pain sensitivity and pain modulation.^{17,99} This brief "bedside" QST testing paradigm will conveniently measure mechanical pain sensitivity (pain threshold), temporal summation of pain (reflecting pain-promoting processes), and conditioned pain modulation (reflecting endogenous pain inhibition). We hypothesize that participants in mindfulness meditation group will achieve greater improvements in pain sensitivity and modulation parameters than those in the CBT group, which may mediate potential differences in treatment effects. For this test, participants will receive pain pressure stimulation from a Somedic pressure algometer, which will be measured using a standard set of weighted probes. Pain threshold and tolerance will be measured on the following sites on both the left and right sides of the body: low back, trapezius, and thumb. Participants will also immerse their hand in a cold water bath twice and rate intensity of the cold pain on a numeric rating scale. This test will be administered by a trained research staff.

Salt Lake City, UT (Site PI: [name]):

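### The protocol conflicts with itself on whether the optional mechanistic tests come before or after allocation at the in-person baseline visit, so their baselines may be taken with the arm known

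*Combined protocol and SAP*

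**What the plan says.** **Timing of the optional tests.** Section 7 (Optional, Additional Testing) says: "The testing will be site-specific, conducted at the end of the two in-person study assessment visits (at baseline and exit". Section 5.6.1 (In-Person Consent) gives the same placement when it introduces the testing, "which would take place at the end of the in-person study visits".

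**Timing of randomisation.** For the in-person baseline visit, Section 7 lists eligibility, consent, questionnaires and the video activity, and continues: "Then participants will be randomized (1:1 block scheme prepared by the study statistician) to the MM or CBT groups, and receive information about details". Table 4 in Section 7.2.2 also puts allocation inside that visit, which it labels "Initial Visit (Screening, Enrollment, Baseline Assessment, Randomization". Section 7.2.1 describes the same visit and ends it with allocation: "Finally, the participant will be randomized to one of the study arms and scheduled for the MM or CBT intervention".

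**When the arm is disclosed.** Under Section 6.2, "participants will break the seal after completing the baseline assessments". Section 6.2 also says that neither participants nor outcome assessors can be blinded.

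**Use of the tests.** Section 9.2.3 attaches a directional between-arm hypothesis to each site's test. For the Boston test it reads: "We hypothesize that participants in mindfulness meditation group will achieve greater improvements in pain sensitivity and modulation parameters than those in the CBT group". Madison (breath counting) and Salt Lake City (emotion regulation and cue reactivity) have parallel hypotheses. In all three cases the difference is put forward as a possible mediator of treatment effects.

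**The concern.** Randomisation balances a baseline measure only if it is taken before anyone can react to the assignment. Breath counting depends on effort. Pain thresholds and cold-pain ratings depend on the participant's report. The emotion-regulation task asks the participant to apply an instructed strategy, so engagement matters there too, although its outcomes are partly physiological. If any of these is measured after the envelope is opened, the baseline can contain a response to the allocation, and the tester may know the arm as well.

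What is at stake is the between-arm comparison of improvement on the three tests, and any mediation argument built on it. A reader of the results could not tell whether a value labelled baseline came before allocation.

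**Working it through.** The check is mainly a comparison of the visit sequences.

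1. **Section 7, in-person baseline:** eligibility, consent, questionnaires, video activity, randomisation, information about the arm and its schedule. The optional test is not in the list.
2. **Section 7.2.2, Table 4, initial visit:** eligibility, consent, enrolment, questionnaires and video activity, randomisation, scheduling, compensation. The optional test is not in the list.
3. **Sections 5.6.1 and 7, optional testing:** the test comes at the end of the in-person visit. Put together with items 1 and 2, the literal order is video activity, randomisation and disclosure, then the optional test.
4. **Section 7.2.1:** baseline assessments, offer of the optional-test consent, then randomisation as the last step. On this text the test, if done that day, would precede allocation. But the section places only the consent, not the test.
5. **Section 6.2:** the seal is broken once the baseline assessments are complete. This would settle the order if the optional test counted as one of them. The only enumeration, in Section 7.2.1, names the questionnaires and the video activity and nothing else.

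Items 3 and 4 cannot both hold literally, because the test and randomisation cannot both end the visit. Item 5 does not resolve the conflict. No sentence states outright that the test comes before allocation, and none states that it comes after.

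**Consequence if the test follows allocation.** Let b be the amount by which knowing the arm shifts the mean baseline score in the MM group relative to the CBT group.

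- Change-score comparison: the bias in (MM change − CBT change) is −b.
- Comparison adjusted for baseline: the bias is −(slope × b), where slope is the regression of exit score on baseline score. A slope below 1 reduces the bias but does not remove it.

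The sign depends on the reaction. On a score where higher is better, suppose MM participants try harder at baseline breath counting. Then b is positive and MM's apparent gain shrinks, against the stated hypothesis. A reaction that lowers the MM baseline relative to CBT would inflate MM's gain.

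The documents give neither b nor the slope, so there is no figure to reproduce and none can be computed.

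**The case against.** The strongest reply is that testing after allocation is an inference. One phrase about timing covers both the baseline and the exit visit, and the exit visit has no randomisation. The phrase may therefore mean only that the test follows the other assessments. Section 5.6.6 describes the optional testing as done at baseline and exit, so counting it among the baseline assessments is reasonable. On that reading Section 6.2 puts it before the envelope, and Section 7.2.1 agrees. The Appendix, which holds the test details and the detailed analysis plan, is not in the text available for review and may fix the order.

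Most of this stands. A reader might infer that the protocol prescribes testing after allocation. The documents do not support that, because Section 7.2.1 points the other way. What survives is that the sections disagree, and that a site following Sections 5.6.1 and 7 as written could test after disclosure.

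Two further inferences also fail. A reader might suppose that agreement to the optional test depends on the arm. However, Section 5.6.1 presents the optional consent within the main consent discussion, and Section 7.2.1 places the offer before randomisation. A reader might also want to convert the problem into an inflated false-positive rate. That needs a size of shift, a baseline-to-exit correlation and an uptake of the optional tests, and the documents give none of them. The direction of the shift is unknown too.

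The tests are optional, specific to one site each and offered only in person. They are not among the objectives in Section 3 or the endpoints in Sections 4.1.1 and 4.1.2. This limits the scope of the point but does not remove it, because each test still carries a stated between-arm hypothesis.

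**Conclusion.** The point holds as an inconsistency about order, with moderate confidence. Sections 5.6.1 and 7, read literally, allow the optional-test baseline to be taken with the arm known to participant and tester. Section 7.2.1 implies the opposite, and Section 6.2 does not decide between them. If testing does follow allocation, the comparison of improvement on the three tests could be biased in either direction, one for one with any shift in a change-score analysis. The documents give no figure from which to size it.

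The conclusion assumes that the Appendix does not already fix the order, and that knowing the assignment can affect performance or report on these tests.

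A reader might extend the concern to the trial's main results, but the documents do not support this. Section 7 has the baseline questionnaires completed before randomisation at both in-person and virtual visits, so the co-primary, secondary and Aim 3 questionnaire measures are untouched.

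**What to change.** Reconcile Section 5.6.1 (In-Person Consent), Section 6.2, Section 7 (the in-person baseline sequence and Optional, Additional Testing) and Section 7.2.1 so that they give one order. State that the optional-test consent and the baseline optional test are completed before the allocation envelope is opened, and that at the exit visit the test comes at the end.

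For participants already tested, record whether the baseline test came before or after allocation. Add a sensitivity analysis of the optional-test comparisons that leaves out baselines taken after allocation.

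The cost is a wording change and a line in the visit checklist. No procedure is added. Section 7 gives each test about 15 minutes on average, so participants who opt in learn their allocation about 15 minutes later. For those already tested, the cost is retrieving the order from site records and one extra analysis.

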7.1 LABS

N/A- No labs will be obtained as part of the study.

7.2 Study Visits

7.2.1 Screening/Baseline:

Potential participants will be identified through the methods described in Section 5.4.1. Potential participants, meeting pre-specified eligibility criteria, will be sent invitation letters with opt-out/response card; those not opting out will be contacted by phone by the study coordinator. Potential participants will also be able to obtain the information about the study through their clinicians, study brochures, and media advertisement, and contact the study coordinator directly to inquire about the study.

A study coordinator will call potential subjects to introduce the study and answer any questions. During this conversation, the researcher will read an informational statement describing the study and informing the participant of the risks and his/her rights as a participant, in particular the right to cease participation at any time without any repercussion or loss of benefits. The researcher will then seek to obtain the participant's verbal consent to proceed with eligibility screening. Screening will be based on self-report and take 10-15 minutes to complete (see Appendix for the scripted text). Those not eligible for or interested in study participation will be referred back to their usual providers.

Those who are eligible and interested will be invited to schedule a virtual or in-person meeting with the study coordinator to complete the screening, enrollment and consent procedures. This meeting will be held virtually or at a clinical or research facility in person. The study participant will be assigned a unique, study-specific ID number, and complete baseline assessments (questionnaires, followed by the videorecorded activity). Enrolled participants will also be given the option to sign an additional consent for optional additional testing, when in person visits are offered (see Section 7, Study Procedures).

Finally, the participant will be randomized to one of the study arms and scheduled for the MM or CBT intervention. A reminder letter, emphasizing the importance of research participation, will be sent to the enrolled participants prior to the intervention start date and/or handed out at the beginning of the intervention course.

For those screened but not enrolled in the study, all identifiable information will be destroyed. We will retain non-identifiable information collected during the screening process to help determine main reasons for ineligibility or declining participation and inform future research. All potential subjects will provide verbal consent for obtaining these data at the beginning of their screening process.

7.2.2 Follow up:

Table 4. Acceptable Window for Study Visits (including weekends)

| Visit | Window | Activities |
|---|--|--|
| Initial Visit (Screening, Enrollment, Baseline Assessment, Randomization) | + up to 12 weeks from the last contact / screening | Virtual or in-person visit. Confirm eligibility; consent/HIPAA authorization form; enrollment; completion of baseline questionnaires and videorecorded activity; randomization; scheduling for the intervention; compensation. |
| 3-month follow-up | + up to 8 weeks from due date | Online/phone/mail (if necessary) questionnaires, compensation mailed |
| 6-month follow-up | + up to 8 weeks from due date | Online/phone/mail (if necessary) questionnaires, compensation mailed |
| 9-month follow-up | + up to 8 weeks from due date | Online/phone/mail (if necessary) questionnaires, compensation mailed |
| 12- month follow-up (exit) | + up to 16 weeks from due date | Virtual or in-person visit. Completion of exit questionnaires and videorecorded activity, compensation. Completion by phone or mail if necessary. |
| In-depth qualitative interview (subset of 80 participants) | + up to 16 weeks from due date | Qualitative interview by phone; compensation mailed. |

The final study visit, the “Exit Visit”, will occur approximately 12 months from the intervention start date for a given participant (Table 4). A subset of participants who completed the final study visit will be invited to undergo an in-depth qualitative interview by phone about their experience with the study intervention and its effects (Table 4).

